7.8 Follow-Up Period

All patients will be followed until death or 3 years after registration, whichever occurs first.

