11.0 STATISTICAL CONSIDERATIONS

11.1 Sample Size with Power Justification

The primary objective of the Phase III study is to compare overall survival (OS) in *EGFR* mutation positive, previously untreated, advanced NSCLC patients randomized to afatinib plus cetuximab versus afatinib alone. The primary objective of the Phase II interim analysis is to evaluate if there is sufficient evidence to continue to the Phase III component by comparing progression-free survival (PFS) between patients randomized to afatinib alone versus afatinib in combination with cetuximab in this study.

Randomization will be stratified by performance status (0-1 versus 2) and *EGFR* mutation type (exon 19 deletion versus L858R mutation). It is assumed that among patients with the exon 19 deletion, the median OS with afatinib alone will be 32 months based on the LUX-Lung 3 and 6 studies. It is also assumed that 56% of patients will have the exon 19 deletion. Further, it is assumed that among patients with the L858R mutation, the median OS with afatinib alone will be 21 months also based on the LUX-Lung studies. The median PFS for patients is assumed to be 13.7 months for patients with the exon 19 deletion and 10.8 months among patients with the L858R mutation among patients randomized to afatinib alone based on the LUX-Lung 3 study.

The addition of cetuximab will be judged to be superior if the true increase in median OS is 45% (hazard ratio = 0.69). A design with 90% power (not adjusting for Phase II analysis) and 0.025 1-sided type I error would require 304 deaths. Assuming exponential survival and uniform accrual, with 48 months of accrual and 14 months of follow-up, this design results in a sample size of 576 eligible *EGFR*-mutant NSCLC patients to detect a 45% improvement in median PFS using a 1-sided 0.025 level stratified log-rank test. Under these design parameters, an observed 25% or greater improvement in median OS (equivalent to an increase in median OS of 8 and 5.5 months for exon 19 and L858R patients will be considered evidence of benefit with the addition of cetuximab to afatinib. Assuming a 5% ineligibility rate, the total target accrual is 605.

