A final interim analysis will take place when 75% of the expected deaths (228) have been observed, which is expected to take place around completion of accrual at 50 months after activation. The same rules for early stopping for either futility or efficacy will be implemented at this analysis. Should no boundaries be crossed, the recommendation will be to continue to full follow-up.

The final analysis will take place upon the observation of 304 deaths (expected around 14 months after completion of accrual) or at maximum of 2 years after the last patient was accrued, whichever comes first. This analysis will be performed using a 1-sided log-rank test, with significance level of 0.024 to account for the interim analyses.

					Approximate HR Boundary	
Analysis	Information	Events	Anticipated accrual n (%)	Study time	Futility	Efficacy
Phase II interim	14% PFS events*	64 PFS	212 (37%)	17 months	1.38	N/A
Phase III interim #1	50% OS events	152 OS	461 (80%)	40 months	1.006	1.56
Phase III interim #2	75% OS events	228 OS	576 (100%)	50 months	1.07	1.44
Final Analysis	100% OS events	304 OS	576 (100%)	62 months	1.25	1.25

* The expected number of PFS events by the end of the Phase III is 446.

c. **REVISED STATISTICAL DESIGN**

Due to the approval of post-first-line regimens and a lower than anticipated accrual rate, the design of the study has been modified. First, the primary endpoint has been changed from OS to PFS to reflect PFS as a relevant endpoint, which also results in a reduction in sample size. In addition, a hard-stop on accrual at a specific time point, even if the accrual target is not met, has been imposed. The following sections lay out the specific details for this new design.

The original design specifies that the Phase II interim analysis to evaluate for stopping for futility will be performed when 64 progression events have been observed, at which time it is expected that 212 eligible patients will have been accrued. In the new design, the sample size for this study has been reduced to the anticipated Phase II sample size of 212 patients with a hard stop in accrual on October 1, 2018, if the accrual to the study has not reached 212 patients.

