The primary objective for the new design is to compare PFS between the arms at the 1-sided 0.025 level. This analysis would take place when 134 PFS events or 70% of the events among eligible patients have been observed (whichever comes first and will depend on sample size attained). With 134 PFS events, this study has 90% power to detect a hazard ratio of 0.57 (75% improvement). The following table describes the analysis as a function of how many patients are accrued by the time of study closure:

Final Sample Size	# events at analysis	HR with 90% power	improvement in PFS
160	112	0.54	85%
180	126	0.56	78%
200	134	0.57	75%
212	134	0.57	75%

An interim analysis will take place when 64 PFS events have been observed. This analysis will be presented to the SWOG Data and Safety Monitoring Committee at the SWOG Group Meeting closest to this number of events. This analysis will evaluate if there is evidence to recommend early stopping of the study for futility by testing the null hypothesis at the 0.5 level, using a stratified log-rank test. If the p-value is 0.5 or greater, than the recommendation will be that there is insufficient evidence to continue accrual to this study.

Secondary Objectives under the revised design are to compare response rates, OS, time to treatment failure (TTF), time to treatment discontinuation (TTD), and toxicity.

Assuming 212 patients enrolled over 36 months with 14 months of additional follow-up, a one-sided log-rank test with an alpha of 0.025 has 90% power to detect an OS hazard ratio of 0.5, corresponding to a 2-fold increase in median OS, under the exponential distribution. Similarly, if it is assumed that the median TTF is 11 months, and the median TTD is also 11 months, there will be 92% power to detect a 70% increase in medians (hazard ratio of 0.59) for each of these endpoints.

Assuming 85% of patients will have measurable disease, 180 patients will be evaluable for the response comparison between arms. Response rates between the arms will be compared using a chi-squared test of independence at the 1-sided 5% level. With 90 patients per arm, this design has 93% power to detect at least a 22% difference in response rates between the arms and within each arm the rates can be estimated to within 10% with 95% confidence.

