11.3 Accrual

The estimated accrual rate is 5-6 patients per month with an assumed 5% ineligibility rate, which will provide the total goal of 223 patients over a 36 month period. However, there will be a hard stop on accrual on October 1, 2018, even if the accrual goal of 212 eligible patients has not been met. In addition, if the study has not accrued 173 patients by April 14, 2018 (the SWOG Spring 2019 meeting), then the study will be closed to further accrual.

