Research Design and Methods: Using a sensitive pyrosequencing assay to measure the *EGFR* T790M mutation (and the original sensitizing mutation), we will test whether the presence of a baseline *EGFR* T790M mutation is correlated with clinical benefit from afatinib plus cetuximab or afatinib alone. This same assay will be used to test whether the *EGFR* T790M mutation emerges during treatment by analyzing post-treatment re-biopsy specimens from patients on both treatment arms. We will also allow quantitatively assess whether the ratio of sensitizing *EGFR* mutation (*EGFRs*) to *EGFR* T790M influences outcome and is altered during treatment. This assay will be performed in the CLIA-certified Yale Cancer Center Tumor Profiling lab by [name] on DNA extracted from formalin-fixed paraffin embedded material. ***The assay is used routinely for clinical purposes at Yale.*** Next generation sequencing approaches for the detection and quantification of *EGFR* mutations will also be used. Tissue submission and T790M results will be monitored on an on-going basis to ensure adequate tissue submission is occurring. We anticipate requiring ~5 unstained tissue sections for this study.

[name] is the key contact for questions regarding this translational medicine study:

[name]
Department of Pathology
Yale University School of Medicine
[name]
[name]
Email: [contact]

Statistical Design:

1. **Evaluate if the presence of de novo EGFR T790M mutation or other molecular alterations in pre-treatment tissue are associated with clinical outcomes.**

Conservatively assuming ~20% of patients will not have baseline assay results due to either assay failure or unusable specimens, we expect assay results from 460 patients at baseline (approximately 230 per arm). With 460 patients, the prevalence of T790M and of the other discrete molecular alterations can be estimated to within 5% with 95% confidence. The probability that at least one T790M mutation is observed assuming the true prevalence is at least 2% is almost 100% (>99%).

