To evaluate if the presence of de novo T790M mutation is associated with primary resistance to afatinib, PFS and OS will be compared between T790M mutation positive and negative patients randomized to the afatinib monotherapy arm using a logrank test stratified by EGFR mutation status (exon 19 deletion vs L858R mutation). Assuming a two-sided alpha of 0.10, the power to detect a 2-fold difference in median OS and PFS, under various scenarios is as follows:

prevalence of de novo T790M mutation	OS HR=0.5	PFS HR=0.5
5%	65%	73%
10%	88%	93%
15%	95%	98%
20%	98%	99%

To evaluate the hypothesis that pre-existing T790M is negatively associated with absolute difference in PFS (and OS) among patients randomized to receive afatinib monotherapy a test of interaction will be performed at the 1-sided 20% level. Assuming the prevalence of the mutation is 20%, the overall treatment hazard ratio is 0.50, the median PFS for afatinib-treated patients with and without the mutation is 6 and 12 months, respectively; and assuming that the true treatment hazard ratio is .34 (a 2.94. fold improvement in median PFS) among T790M patients and the true treatment hazard ratio is .54 (an 85% improvement in median PFS) among patients without the mutation, then this design has 83% power to detect a difference in PFS hazard ratios.

Although preliminary data show a numerical difference in median PFS between patients with exon 19 deletions versus L858R mutations, the difference was not statistically significant. Nevertheless, we will investigate whether de novo T790M mutations are associated with either mutation, using a two-sided Fisher's exact test, and whether there is any difference between these groups. In addition, we will estimate median PFS within each group separately.

To evaluate if the presence of de novo T790M mutation is associated with sensitivity to afatinib plus cetuximab or afatinib alone the response rate will be compared between T790M mutation positive and negative patients using a one-sided Fisher's exact test at the 5% level. Assuming 85% of patients will have measurable disease, then 391 patients will be

included in the analysis of response. This design has at least 89% power to detect a 20% difference in response rates between T790M mutation positive and negative patients assuming the prevalence of the T790M mutation is 20%.

2. Investigate whether the ratio of sensitizing EGFR mutation to EGFR T790 mutation is related to clinical outcomes.

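### The baseline biomarker sample sizes in Section 18.1 (460 assayed, 230 per arm, 391 for response) belong to the abandoned 576-patient design, so most of the powers in 18.1a, b and d are overstated

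*Combined protocol and SAP*

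**What the plan says.** Section 11.1 describes the original overall-survival design: "with 48 months of accrual and 14 months of follow-up, this design results in a sample size of 576 eligible" patients. The revised design in Section 11.2c replaces it: "the sample size for this study has been reduced to the anticipated Phase II sample size of 212 patients". A table there covers final sizes from 160 to 212 ("The following table describes the analysis as a function of how many patients are accrued by the time of study closure"). The secondary clinical powers are restated on the new basis: "Assuming 212 patients enrolled over 36 months with 14 months of additional follow-up". Section 11.3 puts registrations at 223 ("which will provide the total goal of 223 patients over a 36 month period").

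Section 18.1 was not restated in the same way:
- **18.1a (T790M):** after allowing for about 20% assay loss, "we expect assay results from 460 patients at baseline (approximately 230 per arm". Applying an 85% measurable-disease rate, it puts 391 patients in the response analysis. For the interaction test, "then this design has 83% power to detect a difference in PFS hazard ratios".
- **18.1b (copy number):** two power tables with no sample size stated.
- **18.1d (EGFR immunohistochemistry):** again 460 results, 230 per arm.

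Nothing in 18.1 marks these figures as superseded.

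**The concern.** The plan expects more than twice as many assayed patients as the trial will enrol. Section 18.1 is the operative statistical design for the translational objectives. T790M is objective 1.3a and first in the stated order of priority, and 18.1a names a specific hypothesis to be tested; EGFR immunohistochemistry is objective 1.3h.

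If the printed powers are taken at face value, a null T790M result at 10% prevalence would look like strong evidence against a two-fold PFS effect, with an implied 7% chance of missing it. If the true power is much lower, the same result says little.

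**Working it through.** **Origin of the sample sizes**

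| Basis | Assayed (× 0.80) | Per arm | Response (× 0.85) |
|---|---|---|---|
| 576 eligible (original design) | 460.8 | 230 | 460 × 0.85 = 391 |
| 212 eligible (revised design) | 169.6, about 170 | 85 | 170 × 0.85 = 144.5, about 144 |
| 160 eligible (smallest size tabulated in 11.2c) | 128 | 64 | about 109 |

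The plan's 460, 230 and 391 match the first row exactly.

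**T790M log-rank power, afatinib arm (18.1a)**

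Inputs from the plan: two-sided alpha 0.10 (z = 1.645); HR 0.5; a 56/44 split of exon 19 deletion to L858R; median PFS 13.7 and 10.8 months and median OS 32 and 21 months; exponential survival with uniform accrual. I give the medians to T790M-negative patients and twice the hazard to positives.

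- Event probability with accrual A and follow-up F: 1 − [exp(−λF) − exp(−λ(A+F))]/(λA), with λ = ln 2/median.
- Power: Φ(ln 2 × √I − 1.645), where I is the sum over mutation strata of 1/(1/d₁ + 1/d₀), and d₁ and d₀ are the expected events in positives and negatives.

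PFS at 10% prevalence:
- *Old design, n = 230, 48+14 months.* Events (d₁, d₀) are 12.24 and 94.49 for exon 19, and 9.85 and 79.59 for L858R. I = 10.84 + 8.76 = 19.60. Power = Φ(0.693 × 4.427 − 1.645) = Φ(1.42) = 92.3%; the plan prints 93%.
- *Current design, n = 85, 36+14 months.* Events are 4.45 and 33.13, and 3.61 and 28.32. I = 3.92 + 3.20 = 7.12. Power = Φ(0.693 × 2.669 − 1.645) = Φ(0.205) = 58.1%.

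Powers (%) at 5/10/15/20% prevalence:

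| | PFS | OS |
|---|---|---|
| Printed | 73/93/98/99 | 65/88/95/98 |
| Reproduced, n = 230, 48+14 | 72/92/98/99 | 66/88/95/98 |
| n = 85, 36+14 | 38/58/71/79 | 33/51/62/70 |
| n = 85, 3 years each (Section 7.8) | 39/60/72/80 | 35/53/65/73 |
| n = 85, every patient has an event | 40/61/74/82 | – |
| n = 64, 36+14 | 32/48/60/68 | 28/42/52/59 |

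**T790M interaction (18.1a)**

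One-sided alpha 0.20 (z = 0.8416), 20% prevalence, afatinib medians 6 and 12 months, treatment HRs 0.34 and 0.54. Power = Φ(ln(0.54/0.34)/√(Σ 1/d) − 0.8416), summed over four arm-by-marker cells.
- n = 460, 48+14: events 44.4, 34.1, 156.3, 122.4; Σ 1/d = 0.0665; Φ(0.953) = 83%. This matches the printed value.
- n = 170, 36+14: events 16.2, 11.7, 55.3, 41.6; Σ 1/d = 0.189; Φ(0.223) = 59%. The ceiling with every patient progressing is 64%; at n = 128 it is 53%.

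**T790M response (18.1a)**

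Exact one-sided Fisher power, 20-point difference, 20% prevalence. The plan gives no reference response rate, so I assume 40–70%.
- 78 vs 313 patients: 92% or more, consistent with the stated floor of 89%.
- 29 vs 115 patients: 54–59% when positives respond worse; up to 70% when they respond better.

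**Precision and detection (18.1a)**

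- Worst-case half-width 1.96√(0.25/170) = 7.5 points, against 5 stated.
- Chance of seeing at least one mutation at 2% prevalence: 1 − 0.98¹⁷⁰ = 96.8%, against more than 99%.

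**Copy number (18.1b)**

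The printed PFS table (73/93/98/99%) repeats the 18.1a table for 230 patients. The response table (46/76/90/95%) matches one old arm: Fisher at n = 195, assuming 60% vs 30%, gives 46/77/89/95%. The text describes pooled patients. Pooled at current sizes:
- PFS, n = 170: 60/83/93/97%.
- Response, n = 144, same assumed rates: 33/60/78/87%.

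**Immunohistochemistry (18.1d)**

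- Interaction: 61% by the same formula at n = 460, against 64% printed; 43% at n = 170 (ceiling 49%).
- Response, 24-point difference, 19 vs 53 patients by Fisher: 45–66% over assumed rates, against about 90% printed.
- Prognostic PFS (91%) and OS (89%) do not reproduce even at 230 per arm, where both come to about 98%. At 85 per arm they are 71–84% and 68–92%, depending on which H-score group has the plan's medians and on follow-up.

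**The case against.** The three sample sizes and the 18.1a powers are hard to defend; the reasonable objections concern scope and weight.

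- **Immunohistochemistry OS is not shown to be overstated.** The printed 89% lies inside the 68–92% range. Failure to reproduce at 230 per arm is a separate defect, not evidence of the 576-patient origin. This stands, and it is why the conclusion says most powers rather than all.
- **The loss in 18.1b is smaller if arms are pooled.** At 15% and 20% prevalence PFS power is 93% and 97% against 98% and 99%. The plan already warns of low power for HER2 (about 1%) and MET (about 3%). This stands too.
- **The recomputed powers are approximate.** At 5% prevalence, 85 patients contain about four positives, and a large-sample formula is rough there. At 20% prevalence the PFS miss rate is about 21%, not the 42% found at 10%. The ceiling with every patient progressing still leaves a large gap in every row.
- **Response rates are assumed.** True; hence the ranges. No rate tried comes near the printed power for T790M or immunohistochemistry.
- **Little turns on it.** These aims carry no decision rule, and the appendix page is stamped closed in April 2018, so the number actually enrolled may matter more than any projection. That number is not in the documents. Any total at or below 212 eligible makes the printed figures unattainable.
- **It is a failure to update, not faulty multiplication.** Fair: 0.8 × 576 and 0.85 × 460 are computed correctly, from the wrong base.

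**Conclusion.** The concern holds. The sample sizes in 18.1a and 18.1d are inherited from a design the protocol has replaced, and they exceed what 212 eligible patients can supply by a factor of about 2.7 (460/170).

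For T790M at 10% prevalence, the chance of missing a two-fold PFS effect in the afatinib arm is about 40–42%, against the 7% implied. It is about 52% if accrual ended at 160. The interaction test misses its planned effect about 40–41% of the time, against 17%.

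This does not depend on event assumptions. With no assay loss and all 106 patients per arm progressing, PFS power would be 46/69/82/89% and interaction power 69%, still below the printed values.

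The estimates rest on exponential survival, uniform accrual, the plan's medians and 36+14 months; the response figures also rest on assumed rates. The primary PFS analysis is not touched. The repeat-biopsy and exome figures (100 patients, 33 and 50 per arm) do not rest on 460 and are not questioned here.

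**What to change.** 1. In 18.1a and 18.1d, replace 460/230/391 with about 170/85/144 at 212 eligible patients, and note the lower values if accrual stops early (128/64/109 at 160).
2. Restate the dependent powers and precision in 18.1a, b and d, giving the assumed event counts, follow-up and response rates beside each. Alternatively, state the effect detectable with 80% power: with 85 patients and 36+14 months, the T790M PFS hazard ratio is about 0.40 at 10% prevalence and 0.49 at 20%.
3. Say whether the 18.1b tables are pooled or per arm, and recompute them on that basis.
4. Recompute the immunohistochemistry PFS and OS powers from stated medians for each H-score group.

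The cost is rewording in Section 18.1a, b and d. No patients, samples or tests are added; the stated powers become less favourable.

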This preclinical study led to a Phase Ib/II clinical trial of these two agents in *EGFR* mutant NSCLC with acquired resistance to first generation TKIs. Tumors in approximately 30% of patients responded to these agents in combination. (2) Preliminary data from this trial suggests that there is benefit for patients both harboring and lacking T790M. In contrast, afatinib alone, cannot overcome T790M-mediated resistance in preclinical models and in patients.

The prevalence of the *EGFR* T790M mutation in lung adenocarcinoma tumors harboring *EGFR* TKI sensitizing mutations prior to treatment with an *EGFR* TKI is unclear with reports ranging from 0-35%. (3,4,5,6,7,8) It is likely, from evidence available to date, that the presence of pre-existing T790M will negatively influence the outcome to treatment with afatinib but NOT afatinib plus cetuximab. Knowledge of the *EGFR* T790M status in patients prior to treatment is therefore essential for us to determine whether this subset of patients responds differently to afatinib plus cetuximab or afatinib alone. ***Specifically, we will test the hypothesis that the presence of pre-existing T790M will negatively influence the outcome to treatment with afatinib but NOT afatinib plus cetuximab.***

Preliminary Data: Preliminary data from the trial of the combination of afatinib plus cetuximab in patients with acquired resistance to a 1st-generation TKI (erlotinib or gefitinib) suggests that there is benefit for patients both harboring and lacking T790M (see above). ***We, therefore anticipate that the emergence of the EGFR T790M mutation will not be a major contributor to resistance to combination therapy.*** In contrast, we expect that the T790M mutation will emerge in approximately 50% of patients treated with afatinib alone as is seen in patients treated with other single-agent TKIs.

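### Response by T790M status is tested once, across both arms, although the stated hypothesis is that T790M matters on afatinib alone and not on the combination

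*Combined protocol and SAP*

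**What the plan says.** The background to Section 18.1a announces a directional, arm-specific hypothesis: "the presence of pre-existing T790M will negatively influence the outcome to treatment with afatinib but NOT afatinib plus cetuximab".

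Item 1 of the Statistical Design in 18.1a follows it for the time-to-event endpoints. PFS and OS are compared by T790M status among patients randomised to afatinib alone, and a treatment interaction is tested at the 1-sided 20% level.

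The response paragraph of the same item is built differently. To assess "sensitivity to afatinib plus cetuximab or afatinib alone the response rate will be compared between T790M mutation positive and negative patients", and this is done "using a one-sided Fisher's exact test at the 5% level". The size is given as "Assuming 85% of patients will have measurable disease, then 391 patients will be" included in the response analysis, and the power as "at least 89% power to detect a 20% difference in response rates between T790M mutation positive and negative patients" at a T790M prevalence of 20%. No restriction to one arm, no stratification by arm and no interaction term is named for response.

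The sentence promising further comparisons within treatment arms is in Section 18.1b and belongs to the MET, EGFR and HER2 amplification markers. The EGFRs/T790M ratio analysis in 18.1a item 2 has an arm-specific model and an interaction, but for OS and PFS only.

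**The concern.** The question posed is whether T790M matters on one regimen and not on the other. A single comparison of T790M-positive with T790M-negative patients over both arms does not ask that. If the hypothesis is true, about half of the patients in the comparison carry no T790M effect, so the tested difference is diluted and the quoted power does not apply. A significant result could not be assigned to either regimen. A non-significant one would be weak evidence about afatinib alone, which is where the effect is expected. Response would then add little to the arm-specific PFS and OS analyses that it should support.

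**Working it through.** **Inputs.** From 18.1a: 460 assayed patients, about 230 per arm; 85% with measurable disease; 20% prevalence; 20-point difference; one-sided Fisher's exact test at 5%. From Section 2.0: 56% response on afatinib in LUX-Lung 3. The response power statement gives no base rate, so 56% in T790M-negative patients of both arms is an assumption, and it is varied below. From 11.2c: the revised size of 212. The power figures are exact enumerations of the Fisher test, except the interaction, which uses a normal approximation.

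**1. The plan's own figure.** 0.85 × 460 = 391, so both arms are counted; one arm would give 0.85 × 230 ≈ 195. At 20% prevalence, 391 splits into 78 positive and 313 negative. With a 20-point difference, the lowest power over all base rates is 92.1%. So the stated lower bound of 89% holds for the stated test. A two-sided uncorrected normal calculation gives 89.2%, a possible source of the figure. One arm (39 vs 156) has a minimum of 66.6% at the stated level, so the bound needs both arms.

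**2. The same test under the stated hypothesis.** Let T790M lower response by d on afatinib and by 0 on the combination, with 1:1 allocation and equal prevalence in the arms. Then:

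pooled difference = (d + 0)/2 = d/2

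For d = 20 points, the pooled rates are (36% + 56%)/2 = 46% in positives and 56% in negatives.

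| Afatinib-only deficit | Pooled, 78 vs 313 | Afatinib arm, 39 vs 156 |
|---|---|---|
| 20 points | 43% | 67% |
| 30 points | 73% | 95% |
| 40 points | 92% | >99% |

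An afatinib-only deficit of 40 points is needed to give the 20-point pooled difference on which the power was computed. For a 20-point deficit with base rates from 40% to 80%, the pooled test has 43% to 53% and the afatinib arm 67% to 75%. The ordering does not change.

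**3. Localisation.** A 10-point deficit in both arms also gives 46% vs 56% pooled, with the same power (42.6%). The two situations look the same to this test at any sample size.

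**4. Interaction on the response difference.** For 20 points on afatinib and 0 on the combination:

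SE = √(0.36×0.64/39 + 0.56×0.44/156 + 0.56×0.44/39 + 0.56×0.44/156) = 0.124

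At one-sided 20%, power = Φ(0.20/0.124 − 0.842) ≈ 78%. At one-sided 5% it is about 49%.

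**5. Revised size.** The 460 belongs to the former 576-patient design (576 × 0.80 ≈ 460). With 212 patients and the same assumptions, 212 × 0.80 × 0.85 ≈ 144 are evaluable: 29 vs 115 pooled, 14 vs 58 in one arm.

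| Afatinib-only deficit | Pooled, 144 | Afatinib arm, 72 |
|---|---|---|
| 20 points | 19% | 28% |
| 30 points | 35% | 55% |
| 40 points | 54% | 84% |

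- A uniform 20-point effect in both arms has 54% pooled.
- At 10% prevalence, a 20-point afatinib-only effect has 11% pooled vs 15% in the arm.
- Interaction: SE = √(0.2304/14 + 0.2464/58 + 0.2464/14 + 0.2464/58) = 0.206. Power at one-sided 20% = Φ(0.20/0.206 − 0.842) ≈ 55%.
- 95% interval for the afatinib-arm difference: half-width 1.96 × √(0.2304/14 + 0.2464/58) ≈ 28 points.

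**The case against.** - **The hypothesis speaks of outcome, not of response, and it is tested by arm for PFS and OS.** This stands. A reader might infer that the plan has no arm-specific test of the T790M hypothesis; that would be wrong. The gap is confined to response.
- **Objective 1.3a.** A reader might take it as the source of the arm-specific claim. It asks only whether T790M or other alterations influence outcomes, with no direction and no contrast between arms. The hypothesis is in 18.1a alone.
- **Pooling is not stated in words.** This is true, and the phrase naming both regimens could be read as one test per arm. But 391 is the two-arm total, and a single arm does not reach 89% at the stated 5% level. It does so only at about one-sided 20%, which the plan sets for the PFS interaction and not for this test.
- **The effect is diluted, not lost.** This also stands. It is tempting to say that pooling averages the effect away, but the difference is halved, and a large afatinib-only effect would still be found.
- **The pooled test is better if T790M acts equally in both arms** (92% vs 67% at the larger size). That is correct. It is a reason to keep the pooled figure, but the plan's own hypothesis denies that situation.
- **At the revised size the arm-level test is weak as well.** This stands and shapes the remedy: neither test has useful power for 20 points.

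**Conclusion.** The point holds for response only. The plan specifies no within-arm or interaction test of response by T790M, and its single comparison is powered on both arms combined. Under the plan's hypothesis that comparison has about 43% power for a 20-point afatinib-only deficit, against 67% in the afatinib arm with half the patients, and it cannot show in which arm an effect lies. The stated power is not a miscalculation: it holds as a lower bound for 391 patients, but it assumes a 20-point difference in the pooled population. These sizes rest on 20% prevalence, a 56% base rate, balanced arms and no T790M effect on the combination. At 212 patients the figures fall to about 19% and 28%. This is a translational analysis and touches no primary or secondary comparison, so it should be corrected but does not threaten the trial's main conclusions.

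**What to change.** In Section 18.1a, Statistical Design item 1, replace the response paragraph with:

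1. a one-sided 5% Fisher's exact test of response by T790M status within the afatinib arm;
2. the same difference, with its confidence interval, within the combination arm;
3. an arm-by-T790M interaction test for response at the 1-sided 20% level already used for PFS.

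Keep the comparison over both arms as descriptive, and say explicitly that it is pooled. Restate the numbers and power for 212 patients (about 144 evaluable), name the base response rate assumed, and present the arm-level results mainly as estimates with intervals.

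The change is to wording only and needs no new data, visits or patients. The price is a much less favourable stated power and, if T790M in fact acts equally in both arms, the loss of the more powerful pooled test as the formal analysis.
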